5.3. PATIENT EXCLUSION CRITERIA

A patient who meets *any of the following criteria will not be included* in the study:

- (a) Life expectancy <2 years as judged by the investigator;
- (b) Psychiatric or other condition that may interfere with the study;
- (c) Participating in the enrollment or 30-day follow-up phase of another clinical study;
- (d) Known allergy to any device component;
- (e) Coagulopathy or uncontrolled bleeding disorder;
- (f) Contraindication to contrast media or anticoagulants;
- (g) Ruptured, leaking, or mycotic aneurysm;
- (h) Aortic dissection;
- (i) Serum creatinine (S-Cr) level >2.0 mg/dL;
- (j) Traumatic vascular injury;
- (k) Active systemic or localized groin infection;
- (l) Connective tissue disease (e.g., Marfan's Syndrome);
- (m) Recent (within prior three months) cerebrovascular accident or myocardial infarction;
- (n) Prior renal transplant;
- (o) Length of either renal artery to be stented <13mm;
- (p) Significant occlusive disease of either renal artery (>70% stenosis);
- (q) An essential accessory renal artery (supplies more than 25% of the renal parenchyma);[‡]
- (r) Indispensable inferior mesenteric artery;
- (s) Aneurysmal disease of the descending thoracic aorta;
- (t) Clinically significant mural thrombus in the suprarenal segment;[¥]
- (u) Prior iliac artery stent implanted that may interfere with delivery system introduction;
- (v) Unsuitable vascular anatomy;
- (w) Pregnancy (female patient of childbearing potential only);
- (x) Existing renal stent;
- (y) Pre-planned need for concomitant procedure (e.g. surgical conduit for vascular access, hypogastric artery embolization/coil, renal artery angioplasty)

[‡]Patients who undergo prior embolization of an essential accessory renal artery may be considered for trial enrollment.

[¥]Mural thrombus >5mm in thickness over >60% of the aortic circumference.

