6.3. ADDITIONAL EVALUATIONS

Additional evaluations include:

- **Procedural and In-Hospital Evaluations:**
 - Volume of contrast media used;
 - Fluoroscopy time;
 - Total procedure time;[‡]
 - Time in ICU;[§]
 - Estimated blood loss;
 - % requiring blood transfusion;
 - Anesthesia time;[¥]
 - Time to hospital discharge;[£]
- **Mortality**, all-cause and aneurysm-related, within 30 days, at six months, and years 1 through 5;
- **MAE Individual Components** within 30 days, at six months, and years 1 through 5;
- **Composite MAEs** after 30 days ,at six months, and years 1 through 5;
- **Aneurysm Rupture** within 30 days, at six months, and years 1 through 5;
- **Conversion to Open Repair** within 30 days, at six months, and years 1 through 5;
- **Adverse Events** (serious and non-serious) within 30 days, at six months, and years 1 through 5;
- **Distal Blood Flow** pre-discharge and at 30 days, six months, and years 1 through 5 as determined by ankle-brachial index measurements and changes over time.
- **Endograft Performance** (aneurysm sac diameter change from the first post-operative visit; device migration; incidence of endoleak) at 30 days, 6 months, and years 1 to 5;
- **Renal Function** pre-discharge and at 30 days, six months, and years 1 through 5, as assessed by the estimated glomerular filtration rate (eGFR) and changes over time;
- **Renal Stent Graft Patency and Integrity** within 30 days, at six months, and years 1 through 5, as determined by contrast-enhanced CT scan, and as assessed by the independent core laboratory, inclusive of:
 - Patent luminal flow
 - Absence of kinking, stenosis, or occlusion (>60%)
 - Absence of stent fracture
 - Absence of graft failure
 - Absence of renal infarct >30%

[‡]Elapsed time from the first break of skin to final closure (i.e., skin to skin time).

[¥]Elapsed time from the initiation to the end of the anesthesia protocol.

[§]Elapsed time from the first administration of anesthesia to release from the ICU or post-anesthesia care unit providing ICU-level care. If the patient is not admitted to the ICU, this is defined as 0 hours.

[£]Elapsed time from initiation of the procedure to physical discharge from the hospital.

- **Stent Graft (Fenestrated/Bifurcated) Patency and Integrity** within 30 days, at six months, and at years 1 through 5, as determined by contrast-enhanced CT scan, and as assessed by the independent core laboratory, inclusive of:
 - Patent luminal flow
 - Absence of kinking or occlusion

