8.4. SCHEDULE OF MEASUREMENTS

A summary of the tests and measurements to be conducted pre-study/at baseline, operatively, prior to discharge, and during follow-up is illustrated in the following chart.

Schedule of Tests:	Screening/ Baseline	Procedure (Day 0)	Pre- Discharge	1 Month*	6 Months*	1 to 5 Years*
Physical Exam [†]	x		x	x	x	x
Blood Labs [‡]	x		x	x	x	x
Contrast-Enhanced CT Scan [¥]	x			x	x	x
Ankle Brachial Index	x		x	x	x	x
Adverse Events		x	x	x	x	x

[†]The physical exam includes overall health and physical assessment and vital signs.

[figure not shown]
[‡]Blood labs include serum creatinine, blood urea nitrogen, hematocrit, and hemoglobin.

[¥]The baseline high resolution, contrast-enhanced CT scan (2mm or less slice spacing) performed within three months prior to enrollment will be reviewed by the independent core lab for patient eligibility determination. Evaluations of endograft performance, renal stent graft patency and integrity, and stent graft patency and integrity will be made based upon post-operative CT scan evaluations by the core laboratory.

*Follow-up windows are ±2 weeks (1 month visit); ±1 month (6 month visit); ±2 months (Year 1 visit); ±3 months (Years 2 through 5 visits)

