8.6.7. Post-Discharge Follow-up Visits

The patient post-discharge follow-up visits are to occur post-procedurally at **30±14 days** (one month visit), **180±30 days** (six month visit), **365±60 days** (one year visit), **730±90 days** (two year visit), **1095±90 days** (three year visit), **1460±90 days** (four year visit), and **1825±90 days** (five year visit).

- [a] Obtain a blood sample for serum creatinine, blood urea nitrogen, hematocrit, and hemoglobin measurements.
- [b] Perform a physical exam.
- [c] Perform Ankle-Brachial Index testing bilaterally.
- [d] Diagnostic Imaging:
 - **CT Scan:** When a CT Scan is performed, collect it as a high resolution, contrast-enhanced CT scan using the same acquisition parameters required by the Core Lab as for the baseline exam. Forward the CT Scan to the Core Lab identified in §2.2. A copy of the site diagnostic report is requested.
 - As per institutional standard of care, record any other imaging performed and provide a copy of the diagnostic report[s].
- [e] Document any new or discontinued medications (cardiac/circulatory).
- [f] Report any adverse finding from the diagnostic testing, or events that occurred since hospital discharge. If an event is a serious adverse event, provide the additional event details on the **Serious Adverse Event** section of the CRF. See §8.7 for adverse event reporting requirements.

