10.8 ADDITIONAL EVALUATIONS

- 10.8.1 In the event that balance between the treated and control groups is not sufficiently close to allow direct comparison, a multivariable analysis will be done in which the MAE rates between the two groups will be compared with the treatment group, propensity score class, and the covariates for which balance was not satisfactorily achieved. This exploratory analysis will determine if treatment retains statistical significance in the presence of the propensity score class adjustment and covariate adjustment for those covariates unsatisfactorily balanced by the propensity score. Also, special interest will be directed to whether the covariates unsatisfactorily balanced have a statistically significant relationship to the MAE rate.
- 10.8.2 *Procedural and In-Hospital Evaluations:* The need for blood transfusion, estimated blood loss volume, contrast volume, fluoroscopy time, procedure time (and other intraprocedural times), anesthesia time and type, frequency of concomitant procedures, ICU time, and time to hospital discharge will be presented descriptively. Qualitative variables will be presented with rate. Quantitative variables will be presented with mean, standard deviation, median, minimum and maximum.
- 10.8.3 *Mortality:* The proportion of patients with mortality (all-cause and aneurysm-related) will be presented at 30 days and at each subsequent timepoint for which data are available (i.e., six months, and annually at years 1 through 5). A descriptive analysis and a Kaplan-Meier analysis of all-cause and aneurysm-related mortality through 30 days and for late follow-up including 30 days will be presented.
- 10.8.4 *Major Adverse Events (MAE) Individual Components:* The proportion of patients experiencing each category of MAE within 30 days and after 30 days at each subsequent timepoint for which data are available will be presented.
- 10.8.5 *Composite Late MAEs(after 30 days):* The proportion of patients experiencing an MAE after 30 days will be presented at each subsequent timepoint for which data are available. A descriptive analysis and a Kaplan-Meier analysis of the MAE composite will be presented for follow-up through 30 days and for late follow-up including 30 days. The descriptive analysis will present the rates for the composite MAE and each individual adverse event that is part of the composite.

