Incidence of Migration: The occurrence of migration (>10mm movement from the original implant location as determined on the first post-operative scan) will be presented descriptively at each follow-up.

Incidence of Endoleak: The occurrence of endoleak (any type or location, new and persistent) will be presented descriptively at each follow-up.

Incidence of Limb Occlusion: The occurrence of endoleak (any type or location, new and persistent) will be presented descriptively at each follow-up.

10.8.12 *Renal Function Evaluations:* A descriptive analysis of renal function will be done based on serum creatinine levels and calculated estimated glomerular filtration rate (eGFR) at 30 days and at each subsequent timepoint for which data are available. Renal dysfunction will be defined as a reduction in eGFR of >30% from the preoperative value.

10.8.13 *Renal Stent Graft Patency and Integrity:* A descriptive analysis of device patent luminal flow, absence of stent fracture, kinking, stenosis, or occlusion [$>60\%$ luminal obstruction]), absence of graft failure, and absence of renal artery infarct $>30\%$ will be determined by contrast-enhanced CT scan, as assessed by the independent core laboratory at 30 days and at each subsequent timepoint for which

data are available. A determination will be made from the data as to whether the occurrence was associated with an SAE or device malfunction.

- 10.8.14 *Stent Graft (fenestrated/bifurcated) Patency and Integrity:* A descriptive analysis of device patent luminal flow, absence of stent fracture, kinking, or occlusion, and absence of graft failure will be determined by contrast-enhanced CT scan, as assessed by the independent core laboratory at 30 days and at each subsequent timepoint for which data are available. A determination will be made from the data as to whether the occurrence was associated with an SAE or device malfunction.
- 10.8.15 *Secondary Procedures:* A descriptive analysis of secondary procedures for resolution of endoleak, limb occlusion, migration, aneurysm sac expansion, and/or a device defect will be done at 30 days and at each subsequent timepoint for which data are available.

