- d) *Core Lab and Independent Physician Assessor*: The Core Lab is responsible for the processing and assessment of all submitted CT scans preoperatively and imaging postoperatively and for reporting of results. The independent physician assessor is responsible for evaluating the Core Lab processed baseline CT scan to determine patient anatomical suitability for enrollment. In addition, for patients deemed anatomically eligible, the independent physician assessor is responsible for recommending the size of renal stent graft for each artery.
- e) *Data Management Group*: The data management group is responsible for database development, validation, control and management of input from monitored CRFs, maintenance, and reporting for statistical analysis.
- f) *Clinical Events Committee*: The independent clinical events committee will consist of at least three physician members and is responsible for review of events and complications documented on CRFs and in source documents by the study investigators during the trial, and for

- categorization of these events according to the event definitions and primary endpoint criteria in this protocol. Reviews will occur on an ongoing basis throughout the trial as events are reported. The adjudicated events will be reviewed by the Data Safety Monitoring Board.
- g) *Data Safety Monitoring Board (DSMB)*: Consistent with the U.S. FDA guidance document *Establishment and Operation of Clinical Trial Data Monitoring Committees*, Endologix has established a DSMB having pertinent expertise to review on a regular basis adjudicated safety data accumulated and trial progress (i.e., enrollment among groups; completeness and timeliness of data; protocol deviations; etc.) from its ongoing clinical investigations. The DSMB consists of five members, two of which must be physicians with specialty training in endovascular repair. One member of the DSMB is a statistician. The DSMB will be convened to review interim data accumulated during the trial and to render a recommendation for enrollment in the trial: continue; amend; suspend; or, terminate. All action items discussed during the meeting will be documented in the minutes, with agreed upon target completion dates for resolution. The final meeting minutes will be distributed to all DSMB members. Endologix will disclose the recommendations of the DSMB to the US FDA in its annual progress reports to the IDE.

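### Renal stent graft patency is a visit-by-visit CT snapshot that ignores the plan's own occlusion definition and gives no denominator for patients without a contrast CT

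*Combined protocol and SAP*

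**What the plan says.** Section 6.3 lists renal stent graft patency and integrity among the additional evaluations, "as determined by contrast-enhanced CT scan, and as assessed by the independent core laboratory, inclusive of" luminal flow, kinking, stenosis or occlusion (threshold 60%), stent fracture, graft failure and renal infarct over 30%. Section 10.8.13 repeats this as a descriptive analysis that "will be determined by contrast-enhanced CT scan, as assessed by the independent core laboratory at 30 days and at each subsequent timepoint for which" data exist. The note to the schedule in section 8.4 agrees on the source: "Evaluations of endograft performance, renal stent graft patency and integrity, and stent graft patency and integrity will be made based upon post-operative CT scan evaluations".

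Section 8.7.7 defines Stent Graft Occlusion more widely. Either an intervention for occlusion of an aortic or renal stent graft, or a Core Lab report of occlusion, qualifies. Section 10.8.13 does not refer to this definition.

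The schedule in 8.4 marks contrast-enhanced CT at 1 month, 6 months and years 1 to 5. Section 8.6.7 is worded conditionally: "When a CT Scan is performed, collect it as a high resolution, contrast-enhanced CT scan". It sends that scan to the Core Lab and adds for the rest: "As per institutional standard of care, record any other imaging performed and provide a copy of the diagnostic report[s". The Core Lab's remit in 11.1(d) is "assessment of all submitted CT scans preoperatively and imaging postoperatively". At entry, section 5.3 excludes "Contraindication to contrast media or anticoagulants" and serum creatinine above 2.0 mg/dL. Neither has a counterpart during follow-up.

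**The concern.** The device is built to keep the renal arteries open through fenestrations, and section 4.2 treats visceral patency as essential to any endovascular repair of these aneurysms. Section 10.8.13 is the only prespecified analysis of renal graft patency, and it runs to five years.

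Two features can make its figure look better than what happened. First, a snapshot at each scan has no memory: an occlusion treated between scans leaves no trace in the luminal-flow result. Second, a patient without a contrast CT has no patency result, and the plan does not say whether that patient stays in the denominator. Loss of renal perfusion can impair renal function, and impaired renal function may be a reason for a scan to be missing. Missingness could then be linked to the outcome. A reader of the final report could not tell how far either feature had acted.

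**Working it through.** **Step 1. The two definitions applied to one patient.** Suppose a renal graft occludes after the 1-month scan, is reopened, and is open at the 6-month scan. Nominal gaps between scans are 180 − 30 = 150 days, 365 − 180 = 185 days, then about 365 days each year, so there is room for this.

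- Under 8.7.7, this is a stent graft occlusion, because there was an intervention for it.
- Under 10.8.13, flow is patent at 1 month, at 6 months and at every later scan at which the graft is open.

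This discrepancy needs no assumption about contrast use.

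**Step 2. Does another analysis name the event?**

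- Treatment Success (6.2) and Secondary Procedure (8.7.7, 10.8.15) list endoleak, limb occlusion, migration, sac expansion and device defect. Renal graft occlusion is not named.
- Renal Stent Graft Failure (8.7.7) concerns delivery and deployment.
- Renal Failure as a major adverse event needs dialysis or a creatinine rise above 0.5 mg/dL at two consecutive intervals. Renal Dysfunction needs an eGFR fall above 30%. Both measure function, not patency.
- The tables by body system (10.8.8, 10.8.9) have renal and secondary-procedure rows, in which the event may sit without being identified.

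**Step 3. Size of the snapshot effect.** The plan states no expected patency rate. Its trial size reproduces: 82/0.85 = 96.5, rounded up to 97. With 97 patients, each patient with a reopened occlusion who is counted as patent moves the per-patient figure by 1/97 = 1.0 point. If both renal arteries are stented in every patient (an assumption), one artery moves the per-artery figure by 1/194 = 0.5 point.

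**Step 4. Size of the missing-scan effect (illustration).** Assumptions not in the documents: all 97 patients are otherwise scanned, 5 occlusions are seen on CT, and every patient with renal failure lacks a contrast CT. The number without CT, m, is scaled from the 30-day renal failure rates in 10.6.2: 97 × 2/192 = 1.0; twice that, 2.0; and 97 × 6/66 = 8.8, taken as 9.

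- Available-case patency = (97 − m − 5)/(97 − m)
- Unscanned counted as not patent = (97 − m − 5)/97
- Unscanned counted as patent = (97 − 5)/97 = 94.8%

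| m | Available-case | Unscanned not patent | Largest overstatement |
|---|---|---|---|
| 1 | 91/96 = 94.8% | 91/97 = 93.8% | about 1 point |
| 2 | 90/95 = 94.7% | 90/97 = 92.8% | about 2 points |
| 9 | 83/88 = 94.3% | 83/97 = 85.6% | about 9 points |

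A milder case: a quarter of the unscanned patients have lost patency, against 5% of the rest. The overstatement is m × (0.25 − 0.05)/97, which is 0.2, 0.4 and 1.9 points. If the unscanned are like the rest, it is zero.

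**The case against.** A reader might infer that the plan removes patients with renal failure from the patency figures. The documents do not say so. The phrase about available data qualifies timepoints: for mortality, section 10.8.3 writes "at each subsequent timepoint for which data are available (i.e., six months, and annually at years 1 through 5", and mortality needs no CT. The schedule asks for contrast CT at every visit without exempting anyone, and the contrast and creatinine criteria apply at entry only. The renal failure definition also weakens the inference: a patient whose creatinine goes from 1.0 to 1.6 mg/dL at two consecutive intervals meets it, yet stays under the 2.0 mg/dL entry limit. What the documents show is an unspecified denominator.

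A reader might also infer a large bias. For example, take 3.0% occluded among scanned patients, 9.1% with renal failure, none of those scanned and all of them occluded. The true rate is then 0.909 × 3.0% + 9.1% = 11.8%. That combines the 30-day open-surgery rate with extreme assumptions. At the earlier endovascular rate (1.04%) with 30% occluded, the result is 0.9896 × 3.0% + 1.04% × 30% = 3.3%.

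There are partial safeguards. Section 10.2 tabulates evaluations by interval, so missing scans would be visible. Section 10.8.12 reports creatinine and eGFR without CT. The infarct item in 10.8.13 might catch an occlusion that left lasting damage, and that section also asks whether an occurrence was associated with a serious adverse event or device malfunction. None of these restores a reopened occlusion to the patency count, and none says how an unscanned patient is handled. The imputation rules in 10.2 cover the primary endpoints only.

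**Conclusion.** The point holds as a mismatch between 10.8.13 and 8.7.7 and as an unstated denominator. The mismatch follows from the text alone. It is worth 1.0 point per affected patient out of 97, and the number of such patients cannot be known in advance. The missing-scan effect is conditional: it exists only if scans are missed more often in patients who have lost a renal graft. It then favours the device, by 0 to about 9 points under the assumptions above, and by no more than about 2 points if renal failure stays within twice the earlier endovascular rate.

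The evaluation is descriptive and has no hypothesis test. Primary safety, primary effectiveness, alpha and sample size are untouched. The documents do not support a claim that patients with renal failure are excluded by rule, or that reported patency will be badly wrong. The change is still worth making, because it alters a reported device-specific result at little cost.

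**What to change.** In 10.8.13:

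1. Define renal stent graft occlusion in line with 8.7.7, as the first of a Core Lab report of occlusion or of obstruction above 60% (the threshold already in 10.8.13), or an intervention for it.
2. Report cumulative freedom from this event by Kaplan-Meier, per patient, and per artery with intervals that allow for two arteries in one patient. Keep the CT snapshot as supportive. Section 10.8 already plans Kaplan-Meier for mortality and major adverse events.
3. At each visit, state the denominator and tabulate patients not evaluable by contrast CT, by eGFR and dialysis status.
4. Add a sensitivity analysis that counts unevaluable patients with renal failure as not patent. Kaplan-Meier would otherwise censor these patients, so step 2 does not deal with informative missingness.
5. Bring in non-CT evidence under 8.6.7 as site reports, in a sensitivity analysis only. Section 8.6.7 asks for reports of that imaging and does not routinely send the images to the Core Lab.

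This changes analysis text only; it sets no rule on who should be imaged or how. The cost is some extra programming, a mix of evidence sources in the sensitivity analysis, and a patency figure that may be slightly less favourable.

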11. ADMINISTRATIVE PROCEDURES

11.1 RESPONSIBILITIES

- a) *Sponsor*: Endologix is responsible as the Sponsor is to ensure proper site and investigator selection, availability of signed investigator agreements prior to study initiation, availability of regulatory and IRB approval prior to the initiation of the study at any site, and management and monitoring of the study with special attention to verification of all clinical requirements, adherence to protocol, good clinical practices and compliance with applicable government and institutional regulations. Ongoing monitoring visits of the investigational center and hospital records will be conducted to verify the data recorded on the CRFs. Furthermore, the sponsor is responsible for ensuring obtaining proper regulatory approvals, and reporting to regulatory authorities per all applicable regulations.
- b) *Medical Monitor*: The Medical Monitor is responsible for reviewing Serious Adverse Events to provide an independent evaluation of device relatedness, procedure relatedness, and type of SAE.
- c) *Investigators*: Each investigator and study site is required to conduct the clinical investigation in accordance with the protocol, the signed investigator agreement, all applicable laws and Federal regulations and any conditions or restrictions imposed by the reviewing ethics committee. This includes compliance with requirements related to ethics committee or IRB approval and reporting, and proper patient informed consent prior to participation in the study. The investigator is also responsible for protecting the rights, safety, and welfare of the patients under his or her care.

Each investigator is responsible for supervising all procedures conducted under this protocol at his or her institution.

Furthermore, the investigator is responsible for ensuring that data are completely, accurately, and promptly recorded on each patient's CRFs and related documents are available to verify the accuracy of the CRFs, and for ensuring the clinical monitor has access to all necessary records to ensure the integrity of the data.

- d) *Core Lab and Independent Physician Assessor*: The Core Lab is responsible for the processing and assessment of all submitted CT scans preoperatively and imaging postoperatively and for reporting of results. The independent physician assessor is responsible for evaluating the Core Lab processed baseline CT scan to determine patient anatomical suitability for enrollment. In addition, for patients deemed anatomically eligible, the independent physician assessor is responsible for recommending the size of renal stent graft for each artery.
- e) *Data Management Group*: The data management group is responsible for database development, validation, control and management of input from monitored CRFs, maintenance, and reporting for statistical analysis.
- f) *Clinical Events Committee*: The independent clinical events committee will consist of at least three physician members and is responsible for review of events and complications documented on CRFs and in source documents by the study investigators during the trial, and for

- categorization of these events according to the event definitions and primary endpoint criteria in this protocol. Reviews will occur on an ongoing basis throughout the trial as events are reported. The adjudicated events will be reviewed by the Data Safety Monitoring Board.
- g) *Data Safety Monitoring Board (DSMB)*: Consistent with the U.S. FDA guidance document *Establishment and Operation of Clinical Trial Data Monitoring Committees*, Endologix has established a DSMB having pertinent expertise to review on a regular basis adjudicated safety data accumulated and trial progress (i.e., enrollment among groups; completeness and timeliness of data; protocol deviations; etc.) from its ongoing clinical investigations. The DSMB consists of five members, two of which must be physicians with specialty training in endovascular repair. One member of the DSMB is a statistician. The DSMB will be convened to review interim data accumulated during the trial and to render a recommendation for enrollment in the trial: continue; amend; suspend; or, terminate. All action items discussed during the meeting will be documented in the minutes, with agreed upon target completion dates for resolution. The final meeting minutes will be distributed to all DSMB members. Endologix will disclose the recommendations of the DSMB to the US FDA in its annual progress reports to the IDE.
- h) *The Ventana Medical Advisory Board (VMAB)*: Endologix has established the Ventana Medical Advisory Board. The purpose of the VMAB is to provide additional oversight of the Endologix Ventana Clinical Development Program to ensure appropriate monitoring, reporting and management of device related adverse events such that patient safety is optimized and investigators / investigative site health care professionals are provided direct access to necessary information, expert medical advice and timely clinical support. More specifically, the VMAB objectives are to i.) review ongoing clinical events related to device issues, ii.) assess the relatedness of such events to device or procedure, iii.) offer medical opinions on patient treatment to investigators and identify situations that may warrant early intervention, iv.) establish predictors of device related failures and v.) advise and review adjustments to protocol where warranted. The VMAB is distinct from the DSMB in membership and purpose and operates under the guidance provided by the Ventana Safety Surveillance Program document. The VMAB membership is constituted and governed by the VMAB Charter document.
- i) *Biostatistician*: The independent biostatistician is responsible for the development and implementation of the data analysis plan, for conducting the data analysis, and for reporting it per the plan.

